7.7 Week 12 or 24 Visit / End of Treatment Visit

Week 12 or 24 will mark the last dose of SOF/LDV to be administered. In addition, if a subject's participation terminates prior to end of treatment, the assessments may be performed at any end-of-treatment visit.

7.7.1 Liver Staging (End of Treatment):

All subjects will have end of treatment liver staging by the same method used to stage at screening.

7.8 Day of Transplant (for Pre-Transplant subjects): Liver Explant Tissue

Subjects who receive treatment pre-transplant and achieve SVR, but who nonetheless progress to liver transplantation, will have a portion of the explanted liver snap frozen or placed in RNA- *later* on the day of transplant. See Laboratory Manual for processing protocol.

7.9 Post treatment follow up visits

After discontinuation of the study drug, subjects will be followed at post-treatment Week 12 and 24. The visit windows are shown below

- Follow up visits (+/- 14 days)
- Post treatment optional liver biopsy -7 days / +30 days (but can be done outside this window at the investigator's or physician designee's discretion).

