3.2 Prospective Arm

The cohort of pre-transplant patients with cirrhosis due to hepatitis C will be treated with SOF/LDV until LT or for a maximum of 24 weeks. Patients with and without HCC within Milan criteria are eligible. Another cohort of liver transplant recipients with recurrent HCV infection post liver transplant will also be treated with SOF/LDV for a period of 12 weeks (no cirrhosis) or 24 weeks (cirrhosis). Patients with fibrosing cholestatic hepatitis are eligible and will be treated for 12 weeks.

Starting with Day 0, all subjects will receive SOF/LDV for 12 or up to 24 weeks. The total amount of time required to complete all the study visits is approximately 56 - 68 weeks from the screening period through the end of the follow-up visits:

- Up to 8 weeks Screening period
- 12 or 24 week treatment period
- 12 and 24 week post-treatment follow-up visits (SVR12 and SVR24)
- 36 weeks post-treatment to assess late viral relapse

Subjects identified to have mutations leading to SOF or LDV resistance following sequencing and phenotypic analysis will be requested to return at 12-week intervals for up to 36 weeks to determine the time required for the resistant virus to return to background levels.

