3.3.2 Secondary Endpoints

- Correlation of the slope of HCV viral load decline (early viral kinetics) with sustained virologic response at 24 weeks post-treatment (SVR₂₄)
- Proportion of subjects achieving SVR₄ and SVR₂₄ (HCV RNA < LLOQ at 4 and 24 weeks after completion of treatment)
- RVR₄, (RVR₄: HCV RNA < LLOQ at Week 4): Correlation of early viral kinetics with the percentage of subjects achieving RVR₄.
- End of treatment response (ETR: HCV RNA < LLOQ at end of treatment). Correlation of early viral kinetics to the percentage of subjects who achieve ETR.
- Correlation of early viral kinetics to the percentage of subjects who achieve SVR₁₂.
- Viral relapse: Correlation of early viral kinetics with the percentage of subjects who develop viral relapse.
- Differential interferon sensitive gene (ISR) response to therapy in subjects treated for 12 weeks who do and do not attain RVR₄ and SVR.
- Host genetic and proteomic factors in subjects with differential RVR₄ and SVR HCV quasispecies evaluation at baseline and during therapy to determine emergence of resistance subjects who attain RVR₄, and those who achieve SVR.
- HIV and HCV immunologic (adaptive and innate) correlates of SVR and RVR
- Change in liver fibrosis before and after treatment as determined by standard of care liver staging method.

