4.1.2 Secondary Endpoints

Secondary efficacy endpoints include: HCV RNA < LLOQ at 4 and 24 weeks after discontinuation of therapy (SVR₄ and SVR₂₄); viral breakthrough; and relapse.

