4.3 Data Handling Conventions

Missing data can have an impact upon the interpretation of the trial data. Other than the endpoints discussed below, values for missing data will not be imputed.

For the analysis of post-baseline categorical efficacy endpoints, if a data point is missing and is preceded and followed in time by values that are deemed successes, then the missing data point will be termed a success; otherwise the data point will be termed a failure.

Any subject with missing data due to premature discontinuation of the study medication will be considered a failure at the time points on, or following, the date of discontinuation. If no HCV RNA values are obtained after the last dose of study medication, the subject will be considered a treatment failure for the SVR endpoints.

Where appropriate, safety data for subjects that did not complete the study will be included in summary statistics. For example,

- If a subject received study medication, the subject will be included in a summary of adverse events according to the treatment received; otherwise, if the subject is not dosed then they will be excluded from the summary.
- If safety laboratory results for a subject are missing for any reason at a time point, the subject will be excluded from the calculation of summary statistics for that time point. If the subject is missing a pre-dose value, then the subject will be excluded from the calculation of summary statistics for the pre-dose value and the change from pre-dose values.

Values for missing vital signs data will not be imputed; however, a missing Day 0 result will be replaced with a screening result, if available.

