4.4.2 Secondary Analysis

The proportion of subjects with HCV RNA below the LLOQ over time (including SVR endpoints) will be presented.

Descriptive summaries and listings will be provided for additional efficacy evaluations of the proportion of subjects who experience virologic failure and other endpoints of interest including ALT normalization, plasma HCV RNA actual values, and change from baseline. Heterogeneity among the study populations (pre- versus post-transplant, severity of liver disease, type of ARVs, baseline characteristics and others) and limited sample size will preclude us from performing extensive multivariate models to determine predictors of treatment success or failure.

Exploratory regression analyses may be performed to assess the relationship between demographic, baseline characteristics, (including baseline viral load, genotype, age, sex, race, ethnicity, presence/absence of cirrhosis, baseline ALT level, prior treatment experience, response to previous treatment [if applicable], and BMI) and antiviral activity (as measured by HCV RNA log reduction).

Details on efficacy analyses will be described in the statistical analysis plan.

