7.6 Study Visits during treatment

All participants will be seen on days 0, weeks 4, and week 12 EOT, (or week 24 if treated for 24 wks).

- Weeks 4 (+/- 7 days)
- Week 12 [and 16, 20, 24 if applicable] (+/- 10 days)

Plasma HCV RNA will be obtained on each visit. Subjects who fail to achieve >2 log₁₀ HCV RNA drop at this time (unless >2 log drop would be below LLOQ) will be discontinued from therapy unless a review by the PI/Operations Committee determines otherwise.

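### Schedule 11.2 omits post-treatment inputs for the Child-Pugh and MELD scores that define reversal of decompensation in the retrospective arm; a lesser gap is that SVR4 has no scheduled sample

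*Combined protocol and SAP*

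**What the plan says.** **Reversal of decompensation (retrospective arm).** Section 3.1 defines it by Child-Pugh and MELD at last follow-up and evaluates it as time to event because follow-up varies. The study rationale and section 3.0 name it as a purpose of the arm. Section 6.3 sets the post-treatment time points at 3 months and at 6 or more months, and refers to section 11 for the complete list of procedures to capture. Schedule 11.2 is that list for chart data. Schedule 11.3, the one consented visit, contains consent and liver staging only.

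**SVR4.** It is a secondary endpoint in section 3.3.2 ("HCV RNA < LLOQ at 4 and 24 weeks after completion of treatment") and again in section 4.1.2 ("HCV RNA < LLOQ at 4 and 24 weeks after discontinuation of therapy"). Section 7.9 states that "subjects will be followed at post-treatment Week 12 and 24", with a window of 14 days either side. Section 3.2 gives post-treatment weeks 12, 24 and 36. Schedules 11.1 and 11.2 give 3 and 6 months. For missing categorical efficacy data, section 4.3 assigns success "if a data point is missing and is preceded and followed in time by values that are deemed successes" and failure otherwise. Section 4.4.2 adds: "Details on efficacy analyses will be described in the statistical analysis plan".

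**The concern.** Both gaps are outcomes that the plan names but whose data its schedules do not list.

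The decompensation gap is the weightier one. If sites abstract what 11.2 lists, the last INR is at end of treatment, and the time-to-event outcome in 3.1 has no post-treatment score to date an event by. If some sites abstract more, whether a patient has a score depends on the site and on how closely the patient was followed. Section 3.1 seeks a consent waiver so that all treated patients can be included and bias avoided; selective availability of the outcome would work against that.

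For SVR4, a rate would have to be reported either almost wholly by imputation or on very few values.

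**Working it through.** **1. Schedule 11.2 against the scores.** The documents do not list the components. Assumed: MELD = bilirubin, creatinine, INR; Child-Pugh = bilirubin, albumin, INR, ascites, encephalopathy.

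| Item in 11.2 | Day 0 | Wk 4 | Wk 12 | Wk 24 | 3M post | 6M+ post |
|---|---|---|---|---|---|---|
| Bilirubin | X | X | X | X | X | X |
| Creatinine | X | X | X | X | X | X |
| INR | X | – | X | X | – | – |
| Albumin | X | – | X | X | – | X |
| Ascites | – | – | – | – | – | – |
| Encephalopathy | – | – | – | – | – | – |
| MELD inputs (of 3) | 3 | 2 | 3 | 3 | 2 | 2 |
| Child-Pugh inputs (of 5) | 3 | 1 | 3 | 3 | 1 | 2 |

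After treatment, the missing INR alone blocks both scores. Sodium is listed at both post-treatment points, so a MELD that includes it has 3 of 4 inputs and is still incomplete. Child-Pugh cannot be rebuilt at Day 0 either, although a pre-treatment score of 7 or more is an entry criterion for candidates in section 5.1.

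**2. Can another section supply the inputs?** Section 3.1 says the retrospective data mirror those of the prospective arm. That does not supply INR, because 11.1 has no post-treatment INR. Schedule 11.1 has a history and physical at 6 months, a possible source for ascites and encephalopathy, but 11.2 has no matching row. Schedule 11.3 adds liver staging only.

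**3. Timing of post-treatment HCV RNA.** The plan's own visit total reproduces from section 3.2: screening + treatment + longest follow-up = 8 + 12 + 36 = 56 weeks and 8 + 24 + 36 = 68 weeks. The prospective week-12 visit falls at 84 − 14 = 70 to 84 + 14 = 98 days, that is, post-treatment weeks 10 to 14. Its earliest date is 70 − 28 = 42 days after week 4. The end-of-treatment window closes 10 days after its target, 28 − 10 = 18 days before week 4. The retrospective arm starts at 3 months. Scheduled values at post-treatment week 4 are therefore 0 in both arms; the Week 4 columns in section 11 are on treatment.

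**4. Who could have a value near week 4?** Section 7.6 says "Plasma HCV RNA will be obtained on each visit" and lists visits at week 12 and, where applicable, 16, 20 and 24, each ± 10 days. A subject stopped at week 8 who stays on the general schedule (section 8.9) has the Week 12 visit 28 ± 10 days after the last dose. On a 24-week course, the same holds for stops at weeks 12, 16 or 20, although 11.1 has no column for weeks 16 and 20. The instruction in 8.9 to stay on schedule follows the confirmed treatment-failure rule, so these subjects are selected.

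**5. SVR4 if a never-scheduled value counts as missing.** Under 4.3 it is a success only if the values before and after are successes. I took on-treatment week 4, end of treatment, and post-treatment weeks 12 and 24, each as success, failure or missing: 3⁴ = 81 patterns. Imputed SVR4 exceeds SVR12 in 0, equals it in 66 and is lower in 15. It equals SVR12 in all 27 patterns with end-of-treatment success. These are logical cases, not probabilities.

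Illustration with assumed relapse timing, all subjects having end-of-treatment response and all non-responders being relapses: true SVR4 = (SVR12 successes + relapses after week 4)/N, and the imputed value = SVR12 successes/N.
- 46/50 (a column of Table 1): with 0, 1, 2, 3 or 4 late relapses, true SVR4 is 92, 94, 96, 98 or 100%; imputed, always 92%. Difference 0 to −8 points.
- 18/20 (prospective arm at its maximum): with 0, 1 or 2 late relapses, true SVR4 is 90, 95 or 100%; imputed, always 90%. Difference 0 to −10 points.

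**The case against.** **Schedule 11.2 is not the whole abstraction list.** Section 10.6 asks sites to record hospitalizations, anemia needing transfusion or EPO, and death, none of which has a row in 11.2. Pre-treatment Child-Pugh and MELD are entry criteria for candidates, also without rows for the scores. The source is the existing chart. This stands. A reader might infer that the decompensation analysis will have no post-treatment score for anyone; the documents do not support that. What remains is that 10.6 names its items, while nothing asks for post-treatment INR, ascites or encephalopathy.

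**The extra visit may never have been meant for decompensation.** Section 3.0 links it to decompensation, cirrhosis and graft survival, while 3.1 links it to fibrosis alone. Staging-only content fits 3.1. The passages differ and should be reconciled; the content of 11.3 is not by itself an error.

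**SVR4 is minor, and the bias is conditional.** This stands. The documents do not say that a never-scheduled value counts as missing, and section 4.4.2 defers the details. A reader might infer a downward bias of up to 8 or 10 points. That holds only on one reading and with assumed relapse timing; on the other reading there is no imputation bias, only almost no data. Retrospective efficacy has its own definition at 12 or more weeks, so SVR4 may be meant mainly for the prospective arm, but that arm lacks the sample too.

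**Conclusion.** The main point holds for the listed data. Post-treatment INR is listed at 0 of 2 time points in 11.2, and ascites and encephalopathy at none, so neither score in the 3.1 definition can be computed after treatment from the listed items. This assumes the usual score components. Scores may exist for some patients, but the plan does not request their inputs, and how many patients would have one is unknown.

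The SVR4 point holds as a minor one: no value is scheduled 4 weeks after completed treatment in either arm. Values near that time would arise only by chance or in a selected group of early stoppers. If 4.3 is applied, SVR4 cannot exceed SVR12 and counts a relapse between post-treatment weeks 4 and 12 as an SVR4 failure. If it is not, the endpoint has almost no data. Neither gap affects primary SVR12, the relapse endpoint or the sample-size tables.

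**What to change.** **Decompensation.** In 11.2, record from charts INR at 3 months and at 6 months or later (last follow-up), albumin at 3 months, and ascites and encephalopathy grade at Day 0 and at each follow-up. Report the number of patients with a computable score at last follow-up. Reconcile 3.0 and 3.1 on whether the 11.3 visit serves decompensation or only fibrosis.

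**SVR4.** Delete it from 3.3.2 and 4.1.2. If any measured week-4 values are shown, list them descriptively with their number, state the early-stop selection, and do not apply the 4.3 imputation. Adding a post-treatment week-4 sample would also close the gap prospectively, but it means an extra visit and cannot be done for past patients.

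**Cost.** An amendment to the endpoint list and schedule 11.2, a few more chart fields, and the loss of one secondary endpoint. No new blood draw is needed. Some charts will lack INR, ascites or encephalopathy near last follow-up, so the scores will cover only part of the retrospective arm.

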7.10 Early Termination and Early Treatment Discontinuation

Participants who elect to discontinue study drugs prior to treatment completion for medical or personal reasons will be given the option of being followed up at least every 12 weeks for safety and research labs until the end of the study. The participant should have an end of treatment visit scheduled as soon as possible after all therapy is discontinued. Participants with undetectable HCV RNA at the end of treatment should continue to follow the scheduled SVR visits following the date of their last dose of therapy.

For the prospective arm, participants who have detectable HCV RNA at the end of treatment or who relapse post-treatment will be asked to return for visits to determine the persistence of any HCV populations with treatment-emergent substitutions conferring resistance to sofosbuvir. Samples collected will be used to determine the durability of response or the dynamics of any changes in resistance conferring mutations. The reason for any early termination should be documented.

8 STUDY AGENT/INTERVENTIONS: PROSPECTIVE ARM

8.1 Disposition and Dispensation

Study agents will be distributed via the UCSF Investigational Pharmacy according to standard pharmacy procedures.

All drug products will be stored in a securely locked area, accessible only to authorized site personnel. To ensure the stability of the study drug and to ensure proper product identification, the drug product should not be stored in a container other than the container in which they are supplied. Consideration will be given to handling, preparation, and disposal through measures that minimize drug contact with the body. Appropriate precautions will be followed to avoid direct eye contact or exposure through inhalation when handling study drugs.

8.2 Packaging and Labeling of Study Drugs

Each bottle will be individually labeled with the patient ID number, dosing instructions, recommended storage conditions, the name and address of the manufacturer, Investigational Use

Statement (“Caution: New Drug – Limited by Federal [USA] Law to Investigational Use”) and that the agent should be kept out of reach of children.

8.3 Formulation of FDC SOF/LDV

SOF/LDV fixed dose combination (FDC) tablets are orange colored, diamond-shaped, film-coated tablets containing 400 mg of sofosbuvir and 90 mg of ledipasvir. The tablets are debossed with “GSI” on one side and “7985” on the other side. The SOF/LDV FDC tablets contain the following inactive ingredients: lactose monohydrate, copovidone, microcrystalline cellulose, croscarmellose sodium, colloidal silicon dioxide, magnesium stearate, polyvinyl alcohol, titanium dioxide, talc, polyethylene glycol, FD&C yellow # 6 /sunset yellow FCF aluminum lake.

8.4 Storage And Handling of FDC SOF/LDV

SOF/LDV FDC bottles should be stored at room temperature below 30°C (86°F).

8.5 Dosage and Administration of FDC SOF/LDV

SOF/LDV FDC tablet is to be administered once daily with or without food. Each subject must be given instructions to maintain approximately the same daily dosing interval between study drug doses. For missed dose(s) of study medication, subjects will be instructed to take the missed dose(s) of study medication as soon as possible during the same day. Subjects will be cautioned never to double the next dose with a missed dose of study drug under any circumstances.

8.6 Treatment of Participants

All participants will receive 12 or up to 24 weeks of SOF/LDV. SOF/LDV will be administered as a single pill at dose of 400 mg and 90 mg respectively orally once a day. It can be taken with or without food.

If a participant who starts treatment with study drug prior to transplant receives 4 weeks of treatment or less prior to transplant and has detectable HCV at time of transplant, they are eligible to receive full treatment post-transplant.

If a participant who starts treatment with study drug prior to transplant has received more than 4 weeks of treatment prior to transplant, they are NOT eligible to receive full treatment post-transplant, regardless of HCV RNA level at the time of liver transplantation. Therefore, study treatment is discontinued at the time of transplant.

8.7 Dose Modifications/Toxicities

Maximal suppression of HCV replication is most likely accomplished by sustained delivery of antiviral agents at their current recommended doses. Dose reduction, however, would compromise this goal and predispose to the emergence of drug-resistant viral variants. Hence, no dose reduction will be allowed for SOF/LDV. If SOF/LDV is stopped due to toxicity, it must not be restarted.

If treatment with study drug is interrupted for \leq 5 consecutive days for reasons other than drug toxicity (such as discontinuation due to GFR $<$ 30), treatment can be reinitiated and the subject can remain in the trial. However, if treatment is interrupted for $>$ 5 days and/or if study drug is interrupted due to drug toxicity, treatment with study drug should be discontinued.

8.8 Dose Modification for SOF/LDV

SOF/LDV dose modifications will not be permitted. If subject meets safety or virologic criteria for discontinuation, the SOF/LDV will be stopped. If a subject forgets to take the medication at the correct time, it may be taken later in the day; however, no more than a single dose should be taken on any calendar day. The subject should resume the standing dosing schedule on the next day. Any treatment interruption or discontinuation will be recorded including the reason for the interruption or discontinuation.

8.9 Criteria Requiring Discontinuation of SOF/LDV

Subjects will be considered treatment failures and will discontinue SOF/LDV if they meet any of the following criteria while taking study drugs:

- Plasma HCV RNA greater than LLOQ after 2 prior consecutive HCV RNA values less than the LLOQ
- Greater than a $1 \log_{10}$ increase in plasma HCV RNA from nadir
- Less than a $2 \log_{10}$ decline in HCV RNA after 4 weeks of treatment

If any of these should occur in a subject who is currently on study drugs, the subject should return within one week for a confirmatory test. If the confirmatory test also meets the same criteria, the subject will be considered a treatment failure and should be discontinued from therapy. Participants will be referred for other treatment options. The anticipated clinical impact of discontinuation should be discussed in advance if possible, particularly if discontinuation is thought to pose a risk to the overall clinical wellbeing of the subject. Those who are discontinued will continue to follow the general study schedule of assessments unless unwilling to do so, in which case they may be seen at least every 12 weeks for safety and research labs until the end of the study. Subjects will be followed closely for resolution of active laboratory abnormalities or adverse events that are considered related to the study agents prior to starting the revised schedule.

Subjects who meet any of the following laboratory criteria must stop all study medication(s):

- Any Grade 3 or greater rash associated with constitutional symptoms
- Any Grade 4 event assessed as possibly, probably, or definitely related to treatment with SOF or LDV

8.9.1 Treatment Failure Criteria After Stopping SOF/LDV

- Have detectable HCV RNA during the post-treatment period (after having achieved HCV RNA <LLOQ at end of treatment).

